COVER PAGE

Official Study Title: Feasibility of Blood-flow Restriction Training Prehabilitation in Older Adults Awaiting Total Knee Replacement

NCT number: NCT06111690

IRB Approval Date: 09-05-2024

Unique Protocol ID: HSC20210590H

Protocol Template Form

Item 1 UTHSCSA Tracking Number	HSC20210590H
---	--------------

Item 2 Abstract / Project Summary	Provide a succinct and accurate description of the proposed research. State the purpose/aims. Describe concisely the research design and methods for achieving the stated goals. This section should be understandable to all members of the IRB, scientific and non-scientific. DO NOT EXCEED THE SPACE PROVIDED.
--	--

Purpose/Objectives: The overall aim of this research is to demonstrate that preoperative exercises (prehabilitation) using blood-flow restriction training (BFRT) is safe, well tolerated, improves muscle function, decreases functional limitation, and increases physical activity in older adults awaiting total knee replacement (TKR).

Research Design/Plan: This is a single group pre-post design study. Outcomes will be measured at baseline, after 6 weeks of prehabilitation, and 8 weeks after TKR.

Methods: Twenty individuals ≥ 60 years old awaiting TKR due to diagnosis of end-stage knee osteoarthritis who meet the inclusion/exclusion criteria will be invited to participate in a 6 weeks of low-intensity BFRT prehabilitation. We will assess muscle morphology (i.e., cross-sectional area and intramuscular fatty content) using dual x-ray absorptiometry (DEXA) scan, quadriceps muscle strength using an isokinetic dynamometer, a battery of performance-based physical function, self-reported physical function and quality of life, and biomarkers of inflammation using blood serum. Feasibility assessment will be done by looking at safety (i.e., adverse events), compliance, and attrition rate.

Clinical Relevance: The low intensity prehabilitation program using BFRT may lead to improvements in muscle morphology and strength, as well as physical function before TKR. Since muscle weakness and functional limitations experienced preoperatively affect the recovery after TKR, these individuals may experience a significant benefit from our program. Thus, our program may allow patients undergoing TKR to perform daily activities early on postoperatively. Moreover, by increasing physical activity and preventing exacerbation of joint inflammation, our program might impact the general health in older adults after TKR.

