Item 3 Background	
------------------------------	--

Describe past experimental and/or clinical findings leading to the formulation of your study.
 
For research involving unapproved drugs, describe animal and human studies.
 
For research that involves approved drugs or devices, describe the FDA approved uses of this drug/device in relation to your protocol.
	
Preoperative exercises interventions (prehabilitation) have gained increasing attention from researchers in different areas of rehabilitation. Prehabilitation before total joint replacement has shown to reduce postoperative length of stay and increase the likelihood of discharge home instead of a rehabilitation facility. Knee osteoarthritis (KOA) is a debilitating musculoskeletal disorder that affects older adults and its incidence continues to grow. Total knee replacement (TKR) is known as the most successful intervention to improve pain and quality of life in individuals with end-stage KOA. However, the surgery fails to address quadriceps muscle weakness, functional limitations and decreased physical activity experienced by those individuals for years. Most of the functional limitations are due to quadriceps weakness that affects important daily tasks such as ascend-descend stairs, sit-to-stand from a chair, and walk long distances. Several studies have proposed a variety of exercise programs targeting muscle strength and physical function pre- or post-surgery, but their results are inconsistent. We believe that these inconsistencies are due to the exercise intensity prescribed. Older adults with end-stage KOA are at the verge of undergoing TKR, which preclude them from participating in traditional resistance exercises that require at least 70% of the maximal voluntary contraction to improve muscle strength. More recently, low-intensity blood flow restriction training (BFRT) has been introduced to the field of musculoskeletal rehabilitation. BFRT has the potential to improve muscle

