
Item 4
 
Purpose and rationale
 
Insert purpose, objectives and research questions/hypotheses here.
 
If you cut and paste from another document, make sure the excerpted material answers the question
	
Primary outcome: feasibility of BFRT during prehabilitation in older adults awaiting TKR.
 
Secondary outcomes: muscle strength and morphology (i.e., volume and quality), physical function, real-time physical activity and concentration of inflammatory biomarkers.
 
Endpoint: Baseline (T0), after 6 weeks of prehabilitation (T1) and 8 weeks postoperative (T2)
 
Justification for Endpoint: - T0 will provide overall idea on subjects' baseline characteristics of outcome-related data.
 
- T1 will provide data on safety, compliance and attrition rate of the BFRT prehabilitation program, as well as its effect on muscle strength and morphology, physical function, real-time physical activity and concentration of inflammatory biomarkers.
 
- T2 will provide data on the continuing effect of BFRT prehabilitation on muscle strength and morphology, physical function, real-time physical activity and concentration of inflammatory biomarkers postoperatively.
 
Rationale: The low intensity prehabilitation program using BFRT may lead to improvements in muscle morphology and strength, as well as physical function before TKR. Since muscle weakness and functional limitations experienced preoperatively affect the recovery after TKR, this population may experience a significant benefit from our program. Thus, the results of our investigations may allow patients undergoing TKR to perform daily activities early on postoperatively. Moreover, by increasing physical activity and preventing exacerbation of joint inflammation, our program might impact the general health in individuals after TKR.

Item 5 Study Population(s) Being Recruited
 
In your recruitment plan, how many different populations of prospective subjects do you plan to target? Provide number: 1
	
Identify the criteria for inclusion:
	
---	--	--

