Twenty subjects will be performing low-resistance exercise with (BFRT). Intervention will start at least seven days after initial evaluation, so it does not influence measures of real-time physical activity. We will use a log to register exercise completion and to record bilateral knee pain before, during and after each intervention session at the PT-Lab. BFRT will be done using low-resistance (20-30% of 1-repetition maximum) leg extensions, leg curls, and sit-to-stand exercises. Performing exercises at this intensity with the blood flow restricted by a cuff, which maintains arterial inflow while obstructing venous outflow distal to the occlusion site, creating a metabolic environment that alters neuromuscular activity and improve quadriceps muscle volume and strength comparable to traditional high-resistance training ($\geq 70\%$ of 1-repetition maximum) in older adults. BFRT cuff will be placed around subject's thighs prior to exercise. Cuff pressure to be used for the BFRT will be established by placing the cuff on the proximal end of the thigh and inflated until full occlusion is achieved. A portable Doppler will be used to capture auscultatory signal of the posterior tibial artery for this assessment. Based on the pressure (mmHg) used to achieve full occlusion, the BFRT cuff ((B)StrongTM; Park City, UT) will be set up at 50% of that pressure to start the intervention and will progress up to 80% pressure according to subject's tolerance. This adjustment will be done once a week in a PT lab, when subjects will have the BFRT cuff pressure increased by 5-10% and will perform the intervention supervised by a trained researcher. Intervention will consist of 10-minute warm-up on a stationary bike, 4 sets (30, 15, 15, and 15 repetitions) of each proposed exercise bilaterally, and stretching exercises of the lower extremity as cool-down. Subjects will perform a 10-repetition submaximal testing for 1-repetition maximum to estimate the resistance to be used for each exercise. We will use adjustable ankle weights (1-20 pounds) for leg extensions and leg curls, and a weighted vest (3-120 pounds) for sit-to-stand exercise. Total time to complete intervention is ~40 minutes. Subjects will wear BFRT cuffs only during the low-resistance exercise (~15-20 minutes). The maximum time recommended to wear the BFRT cuffs is 20 minutes.

Study visit procedures:

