- Physical Functional Assessment to include self-selected gait speed, timed 5 chair rise, single leg stance time, timed-up and go test, stair ascend/descend test, and 6-minute walk test
- Patient-Reported Outcomes Measurement (PROMIS)
- RAND-36-item Health Quality of Life Survey
- Subjects will be provided with an actigraph monitor device and asked to wear it for one-week to assess a baseline physical activity prior to BFRT sessions

Visit 02 – Visit 07 (Treatment Weeks 1 through Week 6; all procedures completed for research)

One week after baseline visit, subjects will complete 12-18 sessions of low-intensity blood flow restriction training (BFRT), two to three times a week, for six weeks, based on patient willingness/availability. A minimum of 12 sessions is required for study participation. BFRT sessions will be completed as described above at the UT Physical Therapy Research Lab. An exercise and pain log will be completed during and after each intervention session. All training sessions will be provided by qualified providers who are also IRB approved research team members.

Visit 08 (Pre-operative Follow up Week 7; all procedures completed for research)

A pre-operative follow-up visit will be scheduled one week after completion of BFRT intervention sessions. Subjects will be asked to complete the following:

Vital signs

Blood sample will be collected (approx. 30ml) to assess inflammatory biomarkers (research).

Whole-body DEXA scan (research)

Physical Functional Assessment to include self-selected gait speed, timed 5 chair rise, single leg stance time, timed-up and go test, stair ascend/descend test, and 6-minute walk test

Patient-Reported Outcomes Measurement (PROMIS)

RAND-36-item Health Quality of Life Survey

Actigraph monitor provided at the end of Treatment week 6 and collected at time of pre-op follow up Week 7

Visit 09 - Routine Total Knee Replacement Surgery (Routine Standard of Care)

Routine knee surgery will be performed per standard of care. Results will be requested for research purposes

Visit 10 (Post-operative Follow up 8-weeks after TKR surgery; all procedures completed for research)

Same procedures as V08 will be completed

Visit 11 – this is a virtual research visit only. Subjects will be asked to mail actigraph monitoring device by mail in a prepaid envelope provided by the study team. This will qualify as the end of study visit.

Adverse events will be monitored at each visit.

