State the formal and testable null and alternative hypotheses for primary and key secondary endpoints, specifying the type of comparison (e.g., superiority, equivalence or non-inferiority, dose response) and time period for which each endpoint will be analyzed.

Our hypotheses are that:

- our exercise protocol will be safe, compliance with intervention will be >80% of completed exercise sessions, and retention will be >80% of subjects.

- Subjects will demonstrate improvement in muscle strength and morphology, physical function, quality of life, physical activity, and biomarkers of inflammation from T0-T1 (before TKR), which will hold true from T0-T2 (after TKR).

Sample Size Determination

Include number of participants to recruit, screen, and enroll to have adequate power to test the key hypotheses for the study. Provide all information needed to validate your calculations and judge the feasibility of enrolling and following the necessary number of participants.

Due to the exploratory (pilot) nature of the study, we aim to recruit 20 subjects to answer our question on the feasibility of our exercise protocol.

Populations for Analyses

Clearly identify and describe the analysis datasets (e.g., which participants will be included in each).

This is a single group pre-post design. All participants recruited will be assessed regarding compliance, adherence, and safety of our exercise protocol. Data on demographics, biomedical factors, and outcomes measures (i.e., muscle

strength and morphology, physical function, quality of life, physical activity, and biomarkers of inflammation) will be entered in the dataset for each timepoint.

Statistical Analyses

Include analysis of primary efficacy endpoints, secondary endpoints, safety analyses, and any planned interim analyses. Descriptive statistics on adverse events (i.e., joint and/or muscle pain) during exercise sessions and at each timepoint will be provided. Data on secondary outcomes (i.e., muscle strength and morphology, physical function, quality of life, physical activity, and biomarkers of inflammation) will be compared between T0-T1, T0-T2 and T1-T2.

Due to the small sample size (N=20) we will conduct a non-parametric paired difference test (i.e., Wilcoxon signed-rank test) to identify whether those comparisons are statically significant.

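### Changes to T2 combine prehabilitation, knee replacement and recovery in a single group, so they cannot be read as a continuing effect of BFRT

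*Combined protocol and SAP*

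**What the plan says.** The Abstract states the design: "This is a single group pre-post design study". Item 4 sets the assessments at "Baseline (T0), after 6 weeks of prehabilitation (T1) and 8 weeks postoperative (T2") and explains the last one by saying that "T2 will provide data on the continuing effect of BFRT prehabilitation on muscle strength and morphology, physical function, real-time physical activity", and inflammatory biomarkers as well.

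Under Statistical Hypotheses in Item 6, subjects are expected to improve "from T0-T1 (before TKR), which will hold true from T0-T2 (after TKR"). The outcomes named there are strength and morphology, physical function, quality of life, physical activity and biomarkers. Statistical Analyses compares T0-T1, T0-T2 and T1-T2 by Wilcoxon signed-rank test.

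The visit schedule in Item 6 places "Visit 09 - Routine Total Knee Replacement Surgery (Routine Standard of Care") after the pre-operative follow-up (Visit 08) and before the 8-week post-operative follow-up (Visit 10). Item 5 admits only people awaiting primary unilateral replacement.

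On what surgery does, the Background (Item 3) says: "Total knee replacement (TKR) is known as the most successful intervention to improve pain and quality of life in individuals with end-stage KOA". Its next sentence says that surgery does not correct long-standing quadriceps weakness, limited function or low activity.

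**The concern.** The words used for T2 give the result to BFRT, but the design cannot. Anything that happens to the subject between T1 and T2 enters the T0-T2 change, and the largest such event is a knee replacement. The plan contains no control group, historical comparator, adjustment or caveat that would take it out. The Data Analysis Plan mentions stratifying by intervention group, but there is only one group.

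Two wrong conclusions are possible. A gain at T2 may be credited to training when surgery produced it. A retained training gain may also be hidden by a post-operative loss. The Data Analysis Plan intends to use the changes from baseline, including the post-operative one, to size a larger trial. It also gives weight to trends in small p-values. A mixed change taken as a BFRT effect would carry the error into that trial.

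**Working it through.** **Step 1: what each change contains.** Let b1 and b2 be the BFRT effect at T1 and at T2, s the effect of surgery, and c1 and c2 everything else in each interval (post-operative recovery falls in c2).

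- T0-T1 change = b1 + c1
- T1-T2 change = (b2 − b1) + s + c2
- T0-T2 change = b2 + s + c1 + c2

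The third line is the sum of the first two, so the data give two equations for five unknowns. Suppose c1 = 0, which an uncontrolled design cannot show. Then b1 is known, but b2 still appears only in the sum b2 + s + c2. The continuing effect b2 cannot be identified. This does not depend on any effect size.

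**Step 2: direction, by outcome, from the documents.**

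- Quality of life is in the hypothesis, and the RAND-36 includes bodily pain (Secondary Outcomes). The Background says surgery improves both, so s is favourable. The T0-T2 clause can be met with b2 = 0.
- For strength, function and activity, the Background says surgery does not address the deficits. The sign of s + c2 at 8 weeks is open.
- For morphology and biomarkers, the documents give no direction for surgery.

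**Step 3: illustration of size.** The plan has no figure to reproduce. N = 20 rests on the pilot nature of the study, with no effect size, SD or power. The assumptions are b2 = 0; paired T0-T2 changes normal with mean d and SD 1, positive meaning better; exact Wilcoxon signed-rank test; two-sided 0.05. Improvement means p < 0.05 with a positive median change. Pairs are 20, or 0.80 × 20 = 16, the edge of the retention target. Each cell has 6,000 simulated trials, so the standard error is at most √(0.25/6000) = 0.0065.

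| Assumed non-BFRT change d (SD of paired change) | 20 pairs | 16 pairs |
|---|---|---|
| −0.5 | 0% | 0% |
| 0 | 2.4% | 2.1% |
| 0.3 | 24% | 18% |
| 0.5 | 55% | 43% |
| 0.8 | 91% | 81% |

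The table also covers masking, because the test sees only the net change. A retained BFRT gain of 0.5 offset by a surgical loss of 0.5 is the d = 0 row. The same gain against a loss of 1.0 is the d = −0.5 row.

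**Step 4: effect on the future trial.** For two groups, 80% power and two-sided 0.05, n per group = 2(1.96 + 0.84)²/δ². This gives 175 for δ = 0.3, 63 for 0.5 and 25 for 0.8. If a mixed change of 0.8 SD were used when the BFRT share was 0.3 SD, the next trial would plan 25 per group where 175 are needed. These values are also assumptions.

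**The case against.** The strongest reply is that this is a feasibility pilot. Item 4 names feasibility as the primary outcome, the benefit language in the rationale is hedged, T0-T1 is compared separately before surgery, and the Data Analysis Plan speaks of describing changes and disclaims a strict significance threshold. All of that is right, and it limits the consequence. It does not remove the problem: the hypothesis and the T2 justification still attribute the result to BFRT, and the changes are meant to feed a later sample size.

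A reader might infer more than the documents support:

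- That surgery alone could fulfil the whole hypothesis. It cannot, because surgery comes after T1 and cannot cause a T0-T1 gain. Only the clause "which will hold true from T0-T2 (after TKR") is exposed.
- That every T2 outcome is biased upward. The documents support this only for quality of life and pain. For strength, function and activity, the Background points away from a surgical gain.
- That the 55% or 91% is this trial's error rate. It follows from an assumed favourable shift; at 0.3 SD the figure is 24%, and at or below zero it is about 2% or less.
- That a post-operative loss of strength would be reported as BFRT failing. No section says so.
- That both limbs are available for every measure. Training is bilateral ("4 sets (30, 15, 15, and 15 repetitions) of each proposed exercise bilaterally") and the DEXA scan covers both thighs. The strength section does not say that both limbs are tested, and the Visit 08 list, repeated at Visit 10, omits dynamometry. Function, quality of life, activity and biomarkers cannot be split by limb.

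**Conclusion.** The point holds as one of attribution. Neither T0-T2 nor T1-T2 can be called a BFRT effect, and the wording in Item 4 and in the T0-T2 clause of the hypothesis should change. The identification argument needs only the single-group design and the timing of surgery. The percentages are illustrations that rest on assumed effect sizes, normal changes and a two-sided 0.05 rule that the plan does not fix.

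The conclusions on safety, compliance and retention are untouched. Item 6 lists quadriceps function under Primary Outcomes, while Item 4 makes strength and morphology secondary. If the Item 6 label stands, this point weighs more, so the two sections must be reconciled. The Data Analysis Plan also relabels the time points and puts the last one 12 weeks after surgery, against 8 weeks elsewhere. That too must be reconciled before any T2 analysis is described.

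**What to change.** 1. Statistical Hypotheses: limit the improvement hypothesis to T0-T1, note that this comparison is itself uncontrolled, and delete the clause extending it to T2.
2. Item 4: restate T2 as describing status after prehabilitation, knee replacement and recovery.
3. Statistical Analyses and Data Analysis Plan: report T0-T2 and T1-T2 as estimates with confidence intervals, make no claim of a BFRT effect, and state that they will not serve as BFRT effect sizes for the future trial.
4. Report thigh composition separately for the surgical and non-surgical limb. The non-surgical limb has the same training without its own surgery, so it is less contaminated. It is not clean, because the subject is still recovering from an operation.
5. State which limbs undergo strength testing and at which visits. Report strength by limb only if both are tested.

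The cost is wording and one per-limb table from scans already planned. The downside is a weaker stated claim at T2. Splitting the 20 subjects into two arms would not be a practical substitute: with 10 per group, power is about 20% for a 0.5 SD difference and 43% for 0.8 SD.

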biomarkers. The laboratory will use the 'MILLIPLEX® MAP Human High Sensitivity T Cell Magnetic Bead Panel' to assess a panel of 8 inflammatory biomarkers: Interleukin (IL)-1 β , IL-2, IL-5, IL-6, IL-10, IL-12p70, IL-13 and Interferon- γ .^{32,53}

Additional Measures

1) Demographic factors: age, gender, ethnicity, marital and educational status

2) Biomedical factors

a) Medication prescribed and over-the-counter used for pain will be recorded in the medication form. We will record the current and highest dosage of any pain medication used during the last month (when performing pre-intervention evaluation), or during the interval between evaluations.

b) Comorbidity data will be collected using the Cumulative Illness Rating Scale.⁵⁴

c) Body Mass Index will be calculated as the subject's body weight divided by the height squared.

d) Knee Range of Motion will be measured in the supine position utilizing a standard goniometer. The available range of knee flexion and extension will be measured. When measuring passive knee extension, the heel will be elevated on a bolster to ensure the end range of extension is achieved.

e) Knee Pain in both knees (surgical and non-surgical sides) will be measured using an 11-point (0 to 10) numeric scale. The scale will be anchored at one end with the phrase "no pain" (0) and at the other end with the phrase "worst imaginable pain". Subject will be instructed to report the greatest pain during last 24h.^{55,56}

Research personnel will keep track of assessment procedures using a checklist. An exercise log will be used to track delivered exercise sessions. All questionnaires will be self-administered using Redcap.

Although subjects are asked to not participate in any exercise-related program during the study period, research personnel will track exercises performed by subjects on a log.

Study personnel reserve the rights to discontinue delivery of intervention if subject presents with muscle or joint pain that cannot be resolved by administering over-the-counter pain medication.

Research personnel will ensure to follow-up with subjects who have discontinued the study in regards to their recovery from muscle or joint flare-ups due to study intervention to monitor AE, SAE and/or UPIRSOs.

Statistical Considerations

Statistical Hypotheses

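### Structured pain recording is specified for the knee only, while the safety summary covers joint and/or muscle pain, so a low muscle-pain count would be hard to interpret

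*Combined protocol and SAP*

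**What the plan says.** All references are to the combined protocol and SAP.

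- **Item 6, Step-by-Step Methods:** a log is kept to "record bilateral knee pain before, during and after each intervention session at the PT-Lab". The knee is the only pain site named, and no scale is given for the log. The same section places the cuffs around the thighs and prescribes leg extensions, leg curls and sit-to-stands.
- **Item 6, Visit 02 to Visit 07:** "An exercise and pain log will be completed during and after each intervention session". No site is named here, and there is no reading before the session.
- **Item 6, end of the visit list:** "Adverse events will be monitored at each visit". How events are elicited or graded is not stated.
- **Item 6, Additional Measures, 2e:** "Knee Pain in both knees (surgical and non-surgical sides) will be measured using an 11-point (0 to 10) numeric scale", with the instruction "Subject will be instructed to report the greatest pain during last 24h".
- **Item 6, text after Additional Measures:** personnel may stop the intervention "if subject presents with muscle or joint pain that cannot be resolved by administering over-the-counter pain medication". Subjects who discontinue are followed for recovery from muscle or joint flare-ups.
- **Item 6, Statistical Analyses:** "Descriptive statistics on adverse events (i.e., joint and/or muscle pain) during exercise sessions and at each timepoint will be provided".

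**The concern.** The analysis promises a summary of two kinds of pain, but the data collection describes a structured item for only one of them. The other kind, muscle pain, arises where the intervention acts most directly: under and below the cuff, in the muscles being exercised.

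Item 4 names feasibility as the primary outcome, the abstract lists safety as one of its components, and the stated aim is to show that the training is safe and well tolerated. The Statistical Hypotheses section sets figures for compliance and retention (both above 80%) but none for safety. The descriptive pain table therefore carries much of the safety conclusion. If knee pain is asked about at fixed moments in every session and muscle pain is picked up in some other, undescribed way, the two rows of that table are not comparable. A short muscle-pain row could mean little pain or little asking. Session-level symptoms that were not recorded at the time cannot be recovered in the analysis.

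**Working it through.** The plan gives no muscle-pain rate, capture rate or safety threshold, so there is no figure to reproduce. The check sets what the summary needs beside what each source supplies.

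**What the summary needs:** muscle pain, by subject, during sessions and at each timepoint.

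**What each source supplies for muscle pain:**

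1. *Session log, Step-by-Step Methods.* Knee only.
2. *Exercise and pain log, Visit 02 to Visit 07.* Site not stated. It could be wider than the knee, but the only description of the log's pain content is the knee item in Step-by-Step Methods.
3. *Numeric scale, 2e.* Knees only, worst pain in the last 24 hours. It is also missing from the Visit 08 procedure list, which Visit 10 repeats.
4. *Adverse-event monitoring at each visit.* Not limited by site, so it can record muscle pain, but no method is given. The schedule has six treatment visit labels (02 to 07) for 12 to 18 sessions, which is 12/6 = 2 to 18/6 = 3 sessions per label. Whether monitoring happens at every session is therefore unclear.
5. *Discontinuation and flare-up follow-up.* These cover pain that over-the-counter medication does not resolve, and subjects who have discontinued. Milder muscle pain in subjects who continue falls outside both.
6. *RAND-36 bodily pain.* Not site-specific, and given only at assessment visits.

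None of the six specifies a structured muscle-pain reading. Sources 2 and 4 might yield one in practice; the text does not say.

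**Scale of the imbalance**, if all 20 subjects complete their sessions:

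- Sessions: 20 × 12 = 240 to 20 × 18 = 360.
- Knee readings, per knee, at three per session (Step-by-Step Methods): 240 × 3 = 720 to 360 × 3 = 1,080.
- Knee readings, per knee, at two per session (Visit 02 to Visit 07): 240 × 2 = 480 to 360 × 2 = 720.
- Muscle readings specified: none. If the visit-schedule log is wider than the knee, the number is undetermined.

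**Size of any under-count.** Recorded proportion = true proportion × probability of capture. The documents give neither term on the right, so no value follows.

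**Would a muscle item at T0, T1 and T2 close the gap?** No. T0 precedes training. The visit schedule puts T1 one week after the last session, beyond a 24-hour recall. Item 5 describes T1 as immediately after the programme, but even then the recall would reach the last session at most. T2 is eight weeks after surgery, so pain there could not be attributed to training. The session log is where the item is needed.

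**The case against.** The strongest reply is that muscle pain is already a named target of safety monitoring. The Statistical Analyses section lists it among the adverse events, monitoring is scheduled at each visit, and the pain log in the visit schedule is not restricted to the knee. Staff may "discontinue delivery of intervention if subject presents with muscle or joint pain" under the stated condition, and flare-ups are followed up in subjects who discontinue. Qualified team members deliver the sessions, so muscle pain is likely to be noticed. Scoring the diseased joint and treating other symptoms as adverse events is also a coherent choice in end-stage knee osteoarthritis, where the rationale is lower load on the joint. Finally, the log form itself is not among the documents, and risks are referred to the consent document, so a muscle field may exist.

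Much of this stands, and it rules out three stronger readings that a reader might infer:

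- *That muscle pain is never systematically recorded.* The monitoring provision and the unrestricted log wording could both record it.
- *That it is left to spontaneous report.* The monitoring method is undescribed; nothing says it is passive.
- *That it will be under-counted.* This is a plausible risk only. Any numerical example would have to assume a capture rate below 100%, and so would assume its own conclusion.

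The reply does not supply a stated source for the muscle-pain half of the summary. Scoring the knee is a fair choice, but the plan then reports muscle pain alongside it, during sessions, without saying how it is obtained.

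**Conclusion.** The point holds as a mismatch between data capture and the planned safety summary. The plan specifies structured pain items for the knee only, and muscle pain in the cuffed, exercised thighs depends on adverse-event monitoring with no described method. Muscle pain may therefore be ascertained less completely than knee pain, and a low count would be hard to interpret for the safety and tolerability aim. The imbalance spans 240 to 360 sessions under full completion; the effect on the reported frequency cannot be derived.

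The conclusion assumes that the log follows its description in Step-by-Step Methods. If the form already has a muscle-pain field, a sentence saying so would settle the main part of the point, leaving only the reporting and timing changes.

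**What to change.** 1. **Step-by-Step Methods:** extend the log item to bilateral knee pain and bilateral thigh muscle pain, each scored 0 to 10, before, during and after each session.
2. **Visit 02 to Visit 07:** align the log description with that timing and those sites. It now omits the pre-session reading, which any within-session change requires.
3. **Visit schedule:** state how muscle-pain adverse events are elicited and graded, and whether this is done at every session.
4. **Statistical Analyses:** for sessions, report joint pain and muscle pain separately. Show the raw scores before, during and after the session as well as any within-session change, because change alone can subtract soreness carried over from an earlier session.
5. **T0, T1 and T2:** do not use a change-from-pre-session summary, since these visits have no pre-session score. A muscle-pain item there is optional and would not capture pain from training.

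**Cost:** one line on an existing log and a few sentences of text. At an estimated one minute per session, 240 to 360 sessions take 240/60 = 4 to 360/60 = 6 hours over the whole study. The downside is more mild muscle-pain reports in the safety table. The change affects data capture and reporting only, not treatment.
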